6.3 Recruitment

6.3.1 Identification of potential participants

Participants with MCI or early AD will be recruited via various avenues as follows:

Via co-applicants: [name] (Research into Memory Brain Sciences and Dementia, Southmead Hospital); [name] (The Research Institute for the Care of Older People (RICE, Bath, UK)); [name] (Bristol Dementia Wellbeing Service (BDWS)); [name] (NHS General Dental Practices participating in Dental Foundation Training salaried schemes (DFS-GDPr's; 25 Bristol-region)); [name] (General Dental Practitioner (GDP)). These individuals will identify potential participants in their databases or who are in their care and provide them with study information if they are interested in taking part.

Via Avon and Wiltshire Mental Health Partnership (AWP) NHS Trust: Join Dementia Research (JDR) and the North Somerset Memory Service. JDR is an opt-in database where those with dementia or who are interested in acting as controls for dementia studies leave their details. The study details will be posted on this site and those who express an interest through the site will be contacted by study staff following JDR protocols. The AWP North Somerset Memory Service is a clinic for those with a dementia diagnosis. Study information will be provided to the site in formats such as posters and leaflets and the Service will pass these to potential participants identified either at clinic appointments or through database searches by AWP staff.

Via Great Minds (for Dementia): Similar to JDR this is an opt-in database where volunteers willing to contribute to dementia research register their interest. Great Minds is hosted by the Dementias Platform^{UK} (Medical Research Council), and an application to Great Minds to access individuals meeting study criteria will be made.

Via GP practices: using database searches and providing information in an appropriate form for potential participants who are visiting their GP. GP practices will identify potential participants

through data base searches to identify those who have a diagnosis of AD or MCI, and be provided with study information to send to these individuals in a form that appropriate for their practice. The GP practices will also be provided with brief information about the study for their waiting rooms in appropriate formats such as posters and leaflets. Interested participants will be directed to contact the study team for more details

Via Dhek Bhal (South Asian community group), Bristol Black Carers and other community groups: We will provide study information for websites or display in their premises, or that can be communicated by text message/email by the group co-ordinators using the methods agreed with the group co-ordinators/leads. Interested participants will be directed to contact the study team for more details, and we will encourage eligible individuals in this community to participate and will support translation needs.

Appropriate formats of study information prepared with the input of the PPI-Co-app and the study Patient Advisory Group (PAG) will be disseminated to locations/organisations as above, as well as memory cafes and their online equivalents, relevant community boards, clubs with an older demographic (with their permission), online-platforms including online and any other platform/by any other media suggested by the PPI-Co-app/PAG. If the opportunity presents itself study team members will attend memory cafes and/or their online equivalents to talk about the study its aims and what it involves. Easy-read versions of information sheets and consent forms are supplied with this application. These will be used to help explain the study to those who for whatever reason, such as language or literacy level, will find them helpful, however all participants will be provided with the full participant information sheet, all this information will be conveyed prior to consenting, using an interpreter if necessary.

Initial contact:

Interested participants/participant carers will be asked to contact the study team using details on displayed/distributed study information or to leave contact details at the leaflet/information source (e.g. GP practices), or will be approached directly by research nurses at memory clinics/by GP-letter/ by letter from Participant Identification Centres such as the BDWS, RICE, AWP North Somerset Memory Service). During an initial phone-call, the study team will provide more information about the study and answer any questions. If the individual remains keen to take part, the team member will establish if patients have a diagnosis, ask some basic eligibility questions to minimise unnecessary travel where a person could have been identified as unsuitable over the phone, take contact details and send full study information. A follow-up phone-call/email/letter as agreed with the potential participant/carer will answer any questions and a screening appointment booked if appropriate. A letter/email/text will be sent to the patient/carer confirming details.

Participants will be reimbursed standard class travel fares, fuel or taxis to a maximum of £20/visit for attendance at study appointments, travel costs above this threshold will be reimbursed where possible.

6.3.2 Consent

Participants who have expressed an interest in taking part in the study will be sent a copy of the participant information sheet prior to their study appointment in the format that they prefer (paper, electronic). At screening participants will attend Southmead Hospital (Brain Centre) so that dental and cognitive assessments can be performed in a single visit. Prior to any study procedures the cognitive assessor will go through the participant information sheet and take informed consent from the participant with the project partner/carer present, excluding individuals lacking capacity. Informed consent will be captured in written form, and captured on the Easy-read consent form where participants have initially received the Easy-read PIS due to language.

This study involves adults with AD, however we will only enrol those with capacity to consent. While a project partner will be recruited, they will not have to attend every study appointment as this is often not practical or necessary for those with early-stage cognitive-decline; in the pilot study project partners and participants requested that the requirement for the project partner to be present at all participant visits was removed. The project partner will be required to attend the screening appointment before capacity to consent has been confirmed. During the consent process the participant's capacity to consent and ability to (1) retain information long enough to make a decision, (2) understand what the decision relates to and consequences of not deciding, (3) understand the benefits, risks and inconveniences of study-participation, (4) communicate their decision, will be assessed. An autonomous informed and written consent form documenting the patient's decision to participate in the study will be completed prior to screening for study inclusion.

Where the individual's capacity to consent is in doubt, every effort will be made to maximise capacity using simple language/leaflets/drawings. Consent will only be obtained if the clinical psychologist believes the individual is competent to consent.

The project partner(carer/friend) will be involved in all aspects of the consent process and similarly asked to consent to support the participant in the study. Support will include reminding and aiding the participant when attending appointments, and with home-care dental-protocols. Should the carer/friend or participant wish to discuss any matters alone with the clinician this will be arranged.

6.4 Discontinuation/Withdrawal of participants

Each participant has the right to withdraw at any time and information relating to all withdrawals will be recorded. If a participant wishes to discontinue, data collected up until that point will be kept and included in the analysis.

Participants who have initially consented to participate and then lose capacity will be withdrawn from further study procedures. Data collected up until that point will be kept and included in the analysis.

7. SAMPLES – STORAGE AND ANALYSIS OF CLINICAL SAMPLES

Samples of blood and saliva will be collected from each participant at the Brain Centre in Southmead at screening, 6 and 12 months. At each of these visits one standard size tube of blood will be taken (approx. 5-8ml) and saliva will collected by asking the participant to swill a small amount of mouthrinse around their mouth and spit this into a collection pot – maximum 5-10 ml). These samples are taken for the research study only and not as part of any standard care and are for analysis under this protocol to determine bacterial load and variety in the saliva, and levels of immune markers in the blood. Consent for storage and future use of any anonymised unused samples will be sought.

Samples will be collected by the University research team members and stored on University premises frozen pending analysis. Analysis will be undertaken by the University team. Bacterial DNA will be amplified using standard techniques to allow quantification of total bacterial content and identification of key species. Proteins will be extracted from the blood using standard techniques and levels of inflammatory markers determined by ELISA or other similar standard technique for quantifying specific proteins. For the duration of the study only study staff will have access to the

samples, but consent for storage and future use of any anonymised unused samples will be sought. At the end of the study any unused samples with consent for future use will be stored in the research team's laboratories, storage will be indefinite as there is a Human Tissue Licence in place (12200), and the DI will permit storage on their licence pending an NHS REC application to use the samples in a future study.

8. ETHICAL AND REGULATORY CONSIDERATIONS

8.1 Assessment and management of risk

The qualitive assessments (semi-structured interviews) will be undertaken by staff trained by the senior qualitative researcher, questions will not be of an upsetting or disturbing nature, they will simply explore the perceptions of participants receiving the intervention and dentists providing the intervention of its success. Participants will be asked to consent to be approached to take part in the qualitative research when they give informed consent at the start of the study, and both groups will give informed consent for the qualitative research prior to taking part in this. It is highly unlikely that the researcher would come into information that has safeguarding implications.

As indicated in '6.3.2 consent' above, this study will recruit those who have cognitive decline, but clear consent procedures are in place to ensure only those with capacity are recruited, and there are also procedures that will be followed if participants lose capacity to consent during the study. Participants must have a project partner who will consent to this role and support the participant with the study procedures.

The study intervention uses standard dental techniques and will be carried out by qualified dentists in dental practice. Dental assessments by the study team will be carried out by qualified dentists assisted by the dental nurse in appropriate facilities within the Brain Centre. None of the dental treatment should pose any risk above that posed by normal dental care.

The cognitive assessments will be carried out by a trained assessor.

8.2 Safety Reporting

Although unexpected, any adverse events will be recorded and reported in accordance with University Hospitals Bristol's Research Safety Reporting SOP if necessary.

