4.2.2 Intervention – IDC group

IDC (Arm1) participants will be informed they have periodontitis and invited to attend a series of visits (BDH or DFS-GDPr). These appointments may be at Bristol Dental Hospital (BDH), or at a Dental Foundation Scheme-General Dental Practice (DFS-GDPr) accredited to provide postgraduate training to Dental-Foundation-Trainees. Each DFS-GDPr has an appointed, accredited and salaried educational supervisor (ES) responsible for the training of the DFT. The study dental nurse will allocate the study participant to BDH or a DFS-GDPr taking travel time into account as far as possible. Periodontal treatment for these participants will be free of charge.

Dentists providing the intervention for the IDC (Arm1) participants (and ESs) will be given appropriate training/update training in the diagnosis, treatment planning and management of participants according to current UK guidelines [67], and the motivational techniques used successfully previously by the research team to improve participant compliance with oral hygiene regimes. A video of the intervention protocol (below) will also be made and provided for reference. Copies of dental charts taken as routine during the treatment of periodontitis will be provided to the study team.

Prior to implementing the IDC protocol a full periodontal assessment (<2 weeks post-randomisation) will determine the treatment plan and visits required to reach periodontal health (3-5 within the first 3-months).

IDC protocol:

- 1. Behaviour motivation and support for participants to attain and maintain effective plaque removal and reduce gum inflammation by a personalised, tailored oral hygiene regimen and motivational advice to maximise home-compliance [26,69].
- 2. Reduce/eliminate subgingival plaque and calculus with standard mechanical therapies and antibiotics if indicated clinically.
- 3. Address sites that respond poorly by repetition of standard mechanical treatment therapies and/or surgical interventions.
- 4. Deliver supportive periodontal care per current UK-guidelines [67] to maintain oral health

If participants in this arm (IDC) have a dentist we will inform the practitioner of their patient's participation in the study; the participant will attend our sites for the IDC, but their GDP for other routine care. The IDC will be free, and the patient should not incur any additional costs from their regular practice.

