4.2.4 Visits at 6, 12 and 18 months

All participants will be invited to return to the Brain Centre, Southmead Hospital at 6 and 12 months for cognitive and periodontal assessments and to donate samples of blood and saliva. For those participants who remain in the study to 18 months, the 18-month assessment will be cognitive only and conducted over video if possible, with face-to-face assessment used if participants are unable to use a video link.

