Appendix 1 Schedule of Procedures

	Visits						
Procedures	Screening at the Brain	Treatment visits in general dental practice (IDC group only) ¹			assessment		18 Month assessment
	centre	1	2	3	at the Brain centre	at the Brain centre	(virtual if possible)
Informed consent	Х						
Demographics	Х						
Medical history	Х						
Cognitive	Х						
Inclusion/Exclusion							
Dental	Х						
Inclusion/Exclusion							
Provision of electric	X						
toothbrush							
Provision of oral healthcare leaflet	X						
Cognitive Assessments	Х				Х	Х	Х
Dental Assessments	Х				Х	Х	
Blood sample	Х				Х	Х	
Saliva sample	Х				Х	Х	
Randomisation	X ²						
Intervention treatment (IDC group only)		х	Х	х			
Motivational reminders (IDC group only)		X ³	X ³	X ³			
Feedback interview	1					Х	

¹It isn't possible to be entirely prescriptive as to the number of treatments will depend on treatment need and there will be a personal approach. Three is the predicted average number.

²This will actually occur the day after this visit, and the participant contacted by their preferred means to let them know which group they are in and allocate a dental practice if they are in the treatment group

³These will actually be sent regularly until study participation ends

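### No visit in either arm includes a step for asking about adverse events, and the intensive dental care arm has more routes by which an event could reach the study, so few events or a difference between arms could not be interpreted.

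*Protocol*

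**What the plan says.** Section 8.2 (Safety Reporting) is a single sentence: "Although unexpected, any adverse events will be recorded and reported in accordance with University Hospitals Bristol's Research Safety Reporting SOP if necessary". It commits to recording events. It does not say when, by whom, with what questions or over what period.

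Appendix 1 goes down to the level of the toothbrush and the leaflet, and it has a row for "Intervention treatment (IDC group only"). It has no adverse-event row at screening, at the treatment visits, or at 6, 12 or 18 months. Medical history appears at screening only. Sections 4.2 and 4.3 add no such step, and the outcomes in section 3.2 include no measure of harm.

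Section 4.2.2 describes what IDC participants may receive: "standard mechanical therapies and antibiotics if indicated clinically", and then "Address sites that respond poorly by repetition of standard mechanical treatment therapies and/or surgical interventions". An initial periodontal assessment "will determine the treatment plan and visits required to reach periodontal health (3-5 within the first 3-months"). A footnote to Appendix 1 says of the treatments that "Three is the predicted average number". Copies of the charts from this treatment go to the study team.

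Under section 4.2.3, SDC participants carry on with their usual dental care, or with none. The contacts that both arms share are set in section 4.2.4: "All participants will be invited to return to the Brain Centre, Southmead Hospital at 6 and 12 months for cognitive and periodontal assessments". The 18-month assessment is cognitive only and is expected for about 75% of participants (section 4.1).

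**The concern.** A commitment to record events works only if some step brings them to light. Here none is scheduled, so what is recorded depends on what a participant happens to mention and to whom. Participants have mild cognitive impairment or early Alzheimer's disease, and the project partner is required only at the first appointment (sections 6.1.1 and 6.3.2). For most of the study, unprompted recall is a weak source in both arms.

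It is also likely to be weaker in one arm. IDC participants see a treating dentist repeatedly, and that dentist's charts are returned. An SDC participant treated by their own dentist has no comparable channel to the study. Two results would then be hard to read. Few or no events could mean little harm or little asking. More events in IDC could mean more harm or more contact. An analysis plan cannot repair either, because the events would never have been collected.

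There is a smaller risk to blinding. With no collector named, a participant who wants to mention a treatment complication at 6 or 12 months may well tell the study dentist or cognitive assessor, both of whom section 4.3 says are blinded.

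**Working it through.** The plan gives no figure for harms, so there is nothing to reproduce. The check has three parts.

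**1. Where could an event be picked up?**

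| Route | IDC | SDC | Source |
|---|---|---|---|
| Scheduled adverse-event question | none | none | Appendix 1; 4.2; 4.3 |
| Shared study visits to 12 months | 2 | 2 | 4.2.4 |
| Study treatment visits in first 3 months | 3 to 5 | 0 | 4.2.2 |
| Treatment charts sent to the study team | yes | no | 4.2.2; nothing equivalent in 4.2.3 |

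**2. Scheduled contacts after randomisation, to 12 months**

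- SDC: 2.
- IDC: 2 + 3 = 5 up to 2 + 5 = 7.
- Ratio: 5/2 = 2.5 up to 7/2 = 3.5.
- If the initial periodontal assessment is a separate visit, IDC has 6 to 8, and the ratio is 3 to 4.

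Supportive periodontal care would add further IDC visits, but the number is not given. Notice of allocation goes to both arms and is left out. These are ratios of contacts, not of recorded events. Converting one to the other needs the chance that an event is mentioned at a contact, which the protocol does not give.

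**3. What could 25 per arm show with perfect capture?**

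The arm size of 25 is from section 6.2.

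- With zero events, the one-sided 95% upper limit solves (1 − p)^25 = 0.05, so p = 1 − 0.05^(1/25) = 0.113, about 11%.
- The chance of seeing at least one event is 1 − (1 − p)^25. For an assumed true rate of 2% this is 0.40, for 5% it is 0.72, and for 10% it is 0.93.

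These limits come from the sample size, not from the gap in collection. They show that a zero count is weak evidence even when everyone is asked. Incomplete capture weakens it further, by an amount that cannot be calculated here.

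**The case against.** The best defence is that section 8.2 does promise to record any adverse event, under a sponsor SOP that is not shown, and that section 8.3.2 commits the study to GCP. The SOP or the CRFs may say how events are sought. This stands as a limit on the claim. A reader might infer that harms will go unrecorded, or that the study relies on spontaneous reports, but the protocol says neither. What can be said is that the protocol schedules no step, and Appendix 1 is where a trial-specific step would be expected.

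Second, section 8.1 says: "None of the dental treatment should pose any risk above that posed by normal dental care". A reader might take the antibiotics and surgery in section 4.2.2 as contradicting this. They do not. The sentence compares the treatment with normal dental care, not IDC with SDC, and more visits do not make it false. Section 8.1 can stay as it is.

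Third, no comparison of harms between arms is planned, and section 3.2 ties progression to recruitment and data completion. So no specified analysis is distorted. The point concerns how any report of harms could be read.

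Fourth, the isolation of the SDC arm can be overstated. Both arms are told their allocation (section 4.2.1), both attend at 6 and 12 months, and the project partner agrees to support the participant throughout (section 6.3.2). IDC participants can also tell the treating dentist well before month 6. The first three soften the claim of under-recording. The last widens the difference between arms.

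**Conclusion.** The point holds as a gap in data collection. The protocol promises to record adverse events but sets no occasion for asking in either arm, and the IDC arm has 2.5 to 3.5 times the scheduled contacts to 12 months as well as returned charts. Harms may be under-recorded, and recorded more completely in IDC. A low count, or a difference between arms, could not then be interpreted.

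The size of the effect is unknown. A reader might infer a particular multiple of excess events in IDC, but any such figure would rest on capture rates that the protocol does not give. The one firm number is the upper limit of about 11% for zero events in 25 with complete capture. The conclusion assumes that the SOP and CRFs, which are not shown, do not already set an identical enquiry in both arms. If they do, the remedy is simply to put it in Appendix 1.

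**What to change.** - **Appendix 1:** add an adverse-event item at 6 and 12 months, and at 18 months where that visit takes place. Use the same defined questions and the same look-back period in both arms.
- **Who is asked, and by whom:** ask the participant and, where possible, the project partner. An existing study team member other than the blinded dentist and cognitive assessor should do the asking.
- **Question wording:** separate new events from the gum bleeding already required for entry (section 6.1.1), or the item will record the disease itself. Include harms from care received at the participant's own dentist.
- **IDC visits:** have the treating dentists note events on the charts they already return. List these separately from the events collected identically in both arms, and use only the latter for any comparison.
- **Section 8.2:** remove the opening qualifier that calls events unexpected and the closing conditional.

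The cost is a short amendment, one CRF page, a few minutes per visit and more minor events to log. Recall over several months remains imperfect, but it is prompted and the same in both arms.
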